#### 16.3.1.2. Time to COVID-19 Symptom Resolution

An exploratory efficacy endpoint is the time to all COVID-19 symptoms resolution from randomization, in days.

The time to symptoms resolution will be calculated as follows:

- Time to symptom resolution (days) = (Latest post-baseline assessment symptom end date – Date of randomization)

Time to symptom resolution will be calculated using data from COVID-19 Symptom Duration page the eCRF.

Subjects will be censored as follows:

1. If the subject has no post-baseline date, the subject will be censored at the date of first dose of study drug;
2. If the subject's symptoms are ongoing, i.e. no end date recorded, the subject will be censored at the subject's end of study date.

If subject has no COVID-19 symptom at baseline, the subject will be censored at Day 1

#### 16.3.1.3. COVID-19 Symptoms Severity over Time

An exploratory efficacy endpoint is COVID-19 symptom severity over time according to the COVID-19 Symptom assessment page of the eCRF by symptom and across all symptoms.

Missing and "Unknown" severity will not be taken into account in the percentages.

Document:	\[REDACTED]\net\enterprise\Apps\sasdata\SASb\SAS\Atea_Pharmaceuticals\AT-527\SAZ\A63631\Biostatistics\Documentation\SAP\AT-03A-001_V1.0_COVID_SAP_PA7.doc		
Author:	[REDACTED]	Version Number:	V1.0
		Version Date:	15Apr2021
Template No.:	CS_TP_BS016 Revision 6	Reference:	CS_WI_BS005

Effective Date: 02Dec2019

Copyright © 2009, 2010, 2012, 2016, 2018, 2019 [REDACTED] All rights reserved. The contents of this document are confidential and proprietary to [REDACTED] Holdings Inc. and its subsidiaries. Unauthorized use, disclosure or reproduction is strictly prohibited.

#### **16.3.1.4. C-Reactive Protein over Time**

An exploratory efficacy endpoint is the analysis of the CRP over time.

#### **16.3.1.5. Level of IgG and IgM over Time**

An exploratory efficacy endpoint is the level of IgG and IgM over time and change from baseline.

#### **16.3.1.6. Level of SARS-CoV-2 Infectious Virus Titer over Time.**

An exploratory efficacy endpoint is the level of SARS-CoV-2 infectious virus titer over time and change from baseline.

#### **16.3.1.7. Proportion of Subjects With a $\geq$ 1-tier Increase PRI on or Before Day 14**

An exploratory efficacy endpoint is the proportion of subjects with a  $\geq$  1-tier increase PRI on or before Day 14. The PRI is defined as a  $\geq$  1-tier increase from baseline in respiratory support methods required to maintain satisfactory oxygenation ( $\text{SpO}_2 \geq 93\%$ ), using the 6-tier hierarchical scale of Respiratory Support methods.

## COVID-19 Statistical Analysis Plan

## ATEA Pharmaceuticals

### Protocol AT-03A-001

Page 45 of 77

### 16.3.2. ANALYSIS OF EXPLORATORY EFFICACY ENDPOINTS

### 16.3.2.1. NEWS Score $\leq 2$

For the Time to a NEWS score  $\leq 2$  endpoint, the median times will be presented for each treatment group as well as the number and percentage of subjects who achieve a NEWS score  $\leq 2$ .

A Kaplan-Meier curves (product-limit estimate) will be provided by treatment arm for the time to a NEWS score  $\leq 2$  (days).

Kaplan-Meier estimates of the time will be provided at the 25th, 50th (median), and 75th percentiles along with their corresponding two-sided 95% CIs. The estimates of the SEs will be computed using the Greenwood's formula, the CI for the median will be calculated according to Brookmeyer and Crowley (1982), and the CIs for the survival function estimates will be derived from the Kaplan-Meier estimates using the log-log transformation.

The p-value associated with the log-rank test statistic will be provided and compared at the one-sided 0.025 alpha level based on a null hypothesis that there is no difference between the treatment groups and will be presented for descriptive purpose only.

### 16.3.2.2. COVID-19 Symptom Resolution

Same analysis as for NEWS Score  $\leq 2$  will be performed for the COVID-19 symptom resolution.

### 16.3.2.3. COVID-19 Symptom Severity

A shift from baseline to the worst post-baseline observed severity according to the COVID-19 Symptom assessment page of the eCRF by symptom and across all symptoms will be presented.

#### 16.3.2.4. C-Reactive Protein

Change from baseline in CRP will be summarized at the time points required in the schedule of assessments in the protocol. Missing data will not be imputed. CRP will be collected from the central laboratory (if measured).

### 16.3.2.5. Level of IgG and IgM over Time

Change from baseline and in the level of IgG and IgM will be summarized at the time points required in the

Document: \[REDACTED]\net\enterprise\Apps\lsasdata\SASb\SAS\Atea\_Pharmaceuticals\AT-527\SAZ63631\Biostatistics\Documentation\SAP\AT-03A-001\_V1.0\_COVID\_SAP\_PA7.doc

Author: [REDACTED]

Version Date: 15Apr2021

Template No.: CS\_TP\_BS

Copyright © 2009, 2010, 2012, 2016, 2018, 2019 [REDACTED] All rights reserved. The contents of this document are confidential and proprietary to [REDACTED] Holdings Inc. and its subsidiaries. Unauthorized use, disclosure or reproduction is strictly prohibited.

schedule of assessments in the protocol. Missing data will not be imputed.

#### 16.3.2.6. Level of SARS-CoV-2 Infectious Virus Titer over Time

Change from baseline in the level of SARS-CoV-2 Infectious virus titer and percent undetectable will be summarized at the time points required in the schedule of assessments in the protocol. Missing data will not be imputed.

#### 16.3.2.7. Proportion of Subjects with a $\geq$ 1-tier Increase PRI on or Before Day 14

Same analysis as for the primary efficacy endpoint will be performed.

#### 16.3.2.8. Time-weighted Average Change from Baseline in Quantitative SARS-CoV-2

Summary statistics will be computed for each TWACFB endpoint for all patients with baseline data and at least one post-baseline data value within the time-frame over which AUC is computed and for each baseline quantitative SARS-CoV-2 subgroup:

- All subjects who have baseline quantitative SARS-CoV-2 above the limit of quantification.
- All subjects who have baseline quantitative SARS-CoV-2 above the median.
- All subjects who have baseline quantitative SARS-CoV-2 above  $4 \log_{10}$  copies/mL.
- All subjects who have baseline quantitative SARS-CoV-2 above  $6 \log_{10}$  copies/mL.

### 17. SAFETY ENDPOINTS

All safety summaries will be presented by treatment group based on the SAF analysis set. There will be no statistical comparisons of the treatment groups for safety data.

#### 17.1. ADVERSE EVENTS

- Prior AEs are defined as any AE that started or worsened in severity on or after the date of signed informed consent but before the first dose of study drug.

Document: \[REDACTED]\net\enterprise\Apps\sasdata\SASb\SAS\Atea\_Pharmaceuticals\AT-527\SAZ\A63631\Biostatistics\Documentation\SAP\AT-03A-001\_V1.0\_COVID\_SAP\_PA7.doc  
Author: \[REDACTED]

Version Number: V1.0  
Version Date: 15Apr2021

Template No.: CS\_TP\_BS016 Revision 6

Reference: CS\_WI\_BS005

Effective Date: 02Dec2019

Copyright © 2009, 2010, 2012, 2016, 2018, 2019 \[REDACTED] All rights reserved. The contents of this document are confidential and proprietary to \[REDACTED] Holdings Inc. and its subsidiaries. Unauthorized use, disclosure or reproduction is strictly prohibited.

- Treatment emergent AEs (TEAEs) are defined as any AE that started or worsened in severity on or after the first dose of study drug but no later than 28 days after the last dose of study drug. Events considered as possibly related to study drug that occur in follow-up more than 28 days after last study drug will also be considered TEAE.

See APPENDIX 1 for handling of partial dates for AEs. In the case where it is not possible to define an AE as treatment emergent or not, the AE will be classified by the worst case; i.e. treatment emergent.

AEs will be coded using the MedDRA dictionary, version 23.0.

An overall summary of number and percentage of subjects within each of the categories described in the sub-sections below will be provided by treatment group based on the SAF analysis set. Should a subject experience multiple event within a category, the subject will be counted only once for that category.

All AEs (prior and TEAE) will be listed.

### 17.1.1. ALL TEAEs

Number and percentage of subjects with at least one TEAE will be presented by SOC and PT. Should a subject experience multiple events within a SOC or PT, the subject will be counted only once for that SOC or PT.

Number and percentage of subjects with at least one TEAE will be broken down further by maximum severity, relationship to study drug and relationship to non-study drug.

### 17.1.1.1. Severity

Severity will be classified as grade 1 (mild), grade 2 (moderate), grade 3 (severe), grade 4 (potentially life-threatening) or grade 5 (death) according to the definitions described in the Division of AIDS (DAIDS) Table and as reported on the AE page of the eCRF. TEAEs starting after the first dose of study drug with a missing severity will be classified as severe (grade 3). Should a subject experience multiple events within a SOC or PT, only the subject's worst severity will be counted for that SOC or PT.

### 17.1.1.2. Relationship to Study Treatment

Relationship to study treatment, as indicated by the Investigator, will be classified as No Reasonable Possibility or Reasonable Possibility as reported on the AE page of the eCRF.

Document: \\[REDACTED]\net\enterprise\Apps\sasdata\SASb\SAS\Atea\_Pharmaceuticals\AT-527\{SZA63631\}\Biostatistics\Documentation\SAP\AT-03A-001\_V1.0\_COVID\_SAP\_PA7.doc  
Author: [REDACTED] Version Number: V1.0  
Template No.: CS\_TP\_BS016 Revision 6 Reference: CS\_WI\_BS005  
Effective Date: 02Dec2019 Version Date: 15Apr2021

COVID-19 Statistical Analysis Plan

ATEA Pharmaceuticals  
Protocol AT-03A-001  
Page 48 of 77

A “Reasonable Possibility” TEAE is defined as a TEAE with an evidence to suggest a causal relationship between the drug(s) and the AE (e.g., AE is uncommon and known to be strongly associated with drug exposure or is uncommon in the study population, but not commonly associated with drug exposure),, while a “No Reasonable Possibility ” TEAE is defined as a TEAE with no evidence to suggest a causal relationship between the drug(s) and the AE. TEAEs with a missing relationship to study treatment will be regarded as Reasonable Possibility. Should a subject experience multiple events within a SOC or PT, only the subject’s worst relationship will be counted for that SOC or PT.

#### **17.1.1.3. Relationship to Non-Study Treatment**

Relationship to non-study treatment, as indicated by the Investigator, will be classified as not related or related (increasing severity of relationship).

A “Related” TEAE is defined as a TEAE with a relationship to non-study treatment of “reasonable possibility”, and a “Non-related” TEAE is defined as a TEAE with a relationship to non-study treatment of “no reasonable possibility”. TEAEs with a missing relationship to non-study drug will be regarded as related to non-study treatment. Should a subject experience multiple events within a SOC or PT, only the subject’s worst relationship will be counted for that SOC or PT.

#### **17.1.2. ADVERSE EVENTS WITH AN OUTCOME OF DEATH**

TEAEs with an outcome of death are those events which are recorded as “Fatal” on the AE page of the eCRF. A summary of TEAEs with an outcome of death by SOC and PT will be prepared.

A listing of all AEs with an outcome of death will be provided.

#### **17.1.3. SERIOUS ADVERSE EVENTS**

Serious adverse events (SAEs) are those events recorded as “Serious” on the AE page of the eCRF. A summary of serious TEAEs by SOC and PT will be prepared. Should a subject experience multiple events within a SOC or PT, the subject will be counted only once for that SOC or PT.

A listing of all SAEs will be provided

---

Document: \\[REDACTED]\net\enterprise\Apps\sasdata\SASb\SAS\Atea\_Pharmaceuticals\AT-527\ISZA63631\Biostatistics\Documentation\SAP\AT-03A-001\_V1.0\_COVID\_SAP\_PA7.doc  
Author: [REDACTED] Version Number: V1.0  
Template No.: CS\_TP\_BS016 Revision 6 Version Date: 15Apr2021  
Effective Date: 02Dec2019 Reference: CS\_WI\_BS005

Copyright © 2009, 2010, 2012, 2016, 2018, 2019 [REDACTED] All rights reserved. The contents of this document are confidential and proprietary to [REDACTED] Holdings Inc. and its subsidiaries. Unauthorized use, disclosure or reproduction is strictly prohibited.

#### 17.1.4. TEAEs LEADING TO DISCONTINUATION FROM STUDY TREATMENT

TEAEs leading to permanent discontinuation from study treatment are those events recorded as “Drug withdrawal” on the AE pages of the eCRF. A summary of TEAEs leading to permanent discontinuation from study treatment by SOC and PT will be prepared. Should a subject experience multiple such events within a SOC or PT, the subject will be counted only once for that SOC or PT.

A listing of all TEAEs leading to permanent discontinuation from study treatment will be provided.

#### 17.1.5. TEAEs LEADING TO DISCONTINUATION FROM STUDY

TEAEs leading to discontinuation from study are those events reported as “Yes” for the question “Did the AE cause the subject to discontinue from the study?” on the AE pages of the eCRF. A summary of TEAEs leading to discontinuation of study by SOC and PT will be prepared. Should a subject experience multiple such events within a SOC or PT, the subject will be counted only once for that SOC or PT.

A listing of all TEAEs leading to discontinuation from study will be provided.

### 17.2. DEATHS

If any subjects die during the study as recorded on the “Death Details” page of the eCRF, the number and percentage of subjects who died due to COVID-19 as primary cause of death and those who died due to any other primary cause will be summarized by treatment group based on the SAF analysis set. Similarly, the number and percentage of subjects who died due to COVID-19 as secondary cause of death and those who died due to any other secondary cause will be summarized by treatment group based on the SAF analysis set. Death due to COVID-19 will be identified by the study Therapeutic Medical Advisor (TMA) in a blinded fashion before the study DBL.

A listing of all deaths will be provided.

### 17.3. LABORATORY EVALUATIONS (INCL. BLOOD GAS AND COAGULATION)

A serum pregnancy test will be performed at the screening visit, and urine or serum pregnancy test will be performed on Day 1 prior to the first dose and at hospital discharge or early termination. Chemistry (incl. blood gas,

Document: \[REDACTED]\net\enterprise\Apps\sasdata\SASb\SAS\Atea\_Pharmaceuticals\AT-527\SAZ\A63631\Biostatistics\Documentation\SAP\AT-03A-001\_V1.0\_COVID\_SAP\_PA7.doc  
Author: \[REDACTED] Version Number: V1.0  
Template No.: CS\_TP\_BS016 Revision 6 Version Date: 15Apr2021  
Effective Date: 02Dec2019 Reference: CS\_WI\_BS005

Copyright © 2009, 2010, 2012, 2016, 2018, 2019 \[REDACTED] All rights reserved. The contents of this document are confidential and proprietary to \[REDACTED] Holdings Inc. and its subsidiaries. Unauthorized use, disclosure or reproduction is strictly prohibited.

COVID-19 Statistical Analysis Plan

ATEA Pharmaceuticals  
Protocol AT-03A-001  
Page 50 of 77

cardiac related tests), hematology, coagulation and urinalysis will be performed as per the schedule of events (refer to protocol, Section 6.5). A list of laboratory parameters to be included in the outputs is included in [APPENDIX 3](#).

Quantitative laboratory parameters reported as “< X”, i.e. below the lower limit of quantification (BLQ) or “> X”, i.e. above the upper limit of quantification (ULQ), will be converted to X for the purpose of quantitative summaries, but will be presented as recorded, i.e. as “< X” or “> X” in the listings. Observed values will then be standardized (refer to [Section 17.3.1](#)) before being summarized and changes from baseline will be computed based on the standardized observed values.

The parameters which need clinical assessment will only be listed (Direct Bilirubin).

For hematology, only the following key parameters will be summarized: hemoglobin, hematocrit, RBC, platelets, WBC, neutrophils.

The following summaries will be provided by treatment group based on the SAF analysis set for each of chemistry, hematology, coagulation, and urinalysis laboratory parameters:

- Observed and change from baseline in Standard International (SI) units by visit (for quantitative parameters);
- Number and percentage of subjects in each laboratory parameter category by visit (for categorical parameters);
- Shift from baseline to the worst post-baseline observed value during D1-D14 according to the DAIDS toxicity grades (for quantitative parameters with available DAIDS toxicity grades; refer to [Section 17.3.2](#))
- Listing of subjects with at least one post-baseline laboratory observed value meeting a DAIDS toxicity grade  $\geq 3$  (for quantitative parameters with available DAIDS toxicity grades; refer to [Section 17.3.2](#))
- Shifts from baseline to the maximum/minimum post-baseline observed value during D1-D14 according to normal range criteria (for quantitative parameters without DAIDS toxicity grades; refer to [Section 17.3.3](#));
- Maximum post-baseline ALT/AST observed value categorized as  $< 3 \times$  upper limit of normal (ULN),  $\geq 3$  to  $< 5 \times$  ULN,  $\geq 5$  to  $< 10 \times$  ULN or  $\geq 10$  ULN by maximum post-baseline total bilirubin (TBL) observed value categorized as  $< 2 \times$  ULN or  $\geq 2 \times$  ULN;
- Scatter plots of the maximum post-baseline observed value in ALT value by the maximum post-baseline observed value in TBL value, both expressed as multiple of ULN;
- Scatter plots of the maximum post-baseline observed value in AST value by the maximum post-baseline

Document: \\[REDACTED]\net\enterprise\Apps\sasdata\SASb\SAS\Atea\_Pharmaceuticals\AT-527\ISZA63631\Biostatistics\Documentation\SAP\AT-03A-001\_V1.0\_COVID\_SAP\_PA7.doc

Author: [REDACTED] Version Number: V1.0  
Version Date: 15Apr2021

Template No.: CS\_TP\_BS016 Revision 6

Reference: CS\_WI\_BS005

Effective Date: 02Dec2019

Copyright © 2009, 2010, 2012, 2016, 2018, 2019 [REDACTED] All rights reserved. The contents of this document are confidential and proprietary to [REDACTED] Holdings Inc. and its subsidiaries. Unauthorized use, disclosure or reproduction is strictly prohibited.

observed value in TBL value, both expressed as multiple of ULN;

- A listing of subjects with at least one post-baseline observed ALT value  $> 3 \times \text{ULN}$ , AST value  $> 3 \times \text{ULN}$  or TBL value  $\geq 2 \times \text{ULN}$  will be provided.

All laboratory data will be listed.

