6.5. Laboratory Evaluations

Laboratory evaluations will be performed as scheduled in [Table 6-1](#). The investigator or designee will assess each abnormal value to determine if it is clinically significant.

- Chemistry: Sodium, calcium (ionized or total calcium is acceptable per local standard of care), potassium, chloride, magnesium, bicarbonate, glucose, BUN, creatinine, creatinine clearance (Cockcroft-Gault formula), total bilirubin, indirect bilirubin, direct bilirubin, alkaline phosphatase, AST, ALT, albumin, CK (elevation may trigger CK isoenzyme analysis), triglycerides, cholesterol, amylase and lipase
- Hematology: WBC count with differential, red blood cell count, hemoglobin, hematocrit, reticulocyte count, mean corpuscular volume (MCV) and platelet count
- Hemoglobin A1c (glycated hemoglobin; at Screening only)
- Coagulation: Prothrombin time (PT) and INR; Note: Depending on logistics, the laboratory may use the PT to calculate INR and only report the INR to the clinical sites.

Protocol Number: AT-03A-001

- Troponin, N-terminal pro b-type natriuretic peptide (NT-proBNP) and B-type natriuretic peptide (BNP)
- Urinalysis: Color, appearance, specific gravity, pH, leukocyte, protein, glucose, ketones, bilirubin, blood, nitrite, urobilinogen. Microscopic examination may be performed if the urinalysis is abnormal.
- Pregnancy tests (serum or urine) will be performed on female subjects of childbearing potential as specified in [Table 6-1](#).

The total volume of blood withdrawn during the course of the study should not exceed 500 mL. However, it is possible that the total blood donation may be higher if repeat blood samples are required for safety assessments.

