8.2.5. Safety Endpoints

Safety-related comparisons for the two treatments in this trial will include:

- Proportions of subjects experiencing SAEs
- Proportions of subjects with fatal outcomes
- Proportions of subjects experiencing AEs
 - Overall, and by body system as coded by MedDRA
- Proportions of subjects experiencing drug-attributed AEs
- Proportions of subjects experiencing graded laboratory abnormalities
 - With abnormality grades defined in the referenced DAIDS table
- Proportions of subjects discontinuing study for AEs
- Proportions of subjects discontinuing treatment for AEs

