## COVID-19 Statistical Analysis Plan

ATEA Pharmaceuticals  
Protocol AT-03A-001  
Page 66 of 77

- Mean corpuscular volume (MCV) (fL)
- Red blood cells (RBC) (x10E12/L)
- White blood cell (WBC) count total (x10E9/L)
- Absolute neutrophils count (x10E9/L)
- Absolute lymphocyte count (x10E9/L)
- Absolute monocyte count (x10E9/L)
- Absolute eosinophils count (x10E9/L)
- Relative neutrophils count
- Relative lymphocyte count
- Relative monocyte count
- Relative eosinophils count
- Relative basophils count
- Relative reticulocyte count
- Platelet count (x10E9/L)

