## COVID-19 Statistical Analysis Plan

DAIDS Term	Laboratory Test	No Event	Grade 1	Grade 2	Grade 3	Grade 4
Hemoglobin, Low	Hemoglobin (g/L)	Male: $\geq 109$ ; Female: $\geq 104$	Male: 100 to 109; Female: 95 to 104	Male: 90 to < 100; Female: 85 to < 95	Male: 70 to < 90; Female: 65 to < 85	Male: < 70; Female: < 65
WBC, Decreased	White blood cell count total (x10E9/L)	> 2.499	2.000 to 2.499	1.500 to 1.999	1.000 to 1.499	< 1.000
Absolute Neutrophil Count, Low	Absolute neutrophils count (x10E9/L)	> 1.000	0.800 to 1.000	0.600 to 0.799	0.400 to 0.599	< 0.400
Absolute Lymphocyte Count, Low	Absolute lymphocyte count (x10E9/L)	$\geq 0.650$	0.600 to < 0.650	0.500 to < 0.600	0.350 to < 0.500	< 0.350
Platelets, Decreased	Platelet count (x10E9/L)	$\geq 125.000$	100.000 to < 125.000	50.000 to < 100.000	25.000 to < 50.000	< 25.000

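### SAP 17.3 leaves absolute lymphocyte count, alone among the five DAIDS-graded haematology tests, out of the by-arm laboratory summaries, so the planned summary of graded abnormalities is incomplete (minor)

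*SAP*

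**What the plan says.** Protocol 8.2.5 lists, among the safety comparisons of the two treatments, "Proportions of subjects experiencing graded laboratory abnormalities", and adds: "With abnormality grades defined in the referenced DAIDS table". Protocol 8.4 says these proportions will be summarised by treatment group, mainly descriptively. Protocol 6.5 collects the data: "Hematology: WBC count with differential".

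SAP 17.3 points to Appendix 3 for scope: "A list of laboratory parameters to be included in the outputs is included in" that appendix, and absolute lymphocyte count is one of the haematology entries there. The section then narrows what is tabulated: "For hematology, only the following key parameters will be summarized: hemoglobin, hematocrit, RBC, platelets, WBC, neutrophils".

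Its by-treatment outputs include a shift from baseline to the worst value over Days 1 to 14 by DAIDS grade, and a listing of subjects with a grade 3 or higher value. Both are described as applying "for quantitative parameters with available DAIDS toxicity grades". Appendix 4 supplies those grades and has a row headed "Absolute Lymphocyte Count, Low" with cut-offs for Grades 1 to 4.

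The Changes to Planned Statistical Analyses Form of 16 March 2022 puts the laboratory evaluations summary among the SAP items that will not be presented. It limits Part B to listings and says the SAP itself will not be revised.

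**The concern.** The plan collects lymphocyte counts, names them for the outputs and sets out their grades, then leaves them off the list of haematology tests to be summarised. The SAP text available gives no reason.

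The endpoint is a proportion of subjects with graded abnormalities. For lymphocytes the plan as written would give no numerator, denominator or percentage by arm. The other white-cell tests do not fill the gap, since a severe lymphocyte grade can coexist with ungraded WBC and neutrophil values (shown in the check). Exclusion criterion 18 limits total WBC and neutrophils at entry but sets no lymphocyte limit, so some subjects may start low. For them a baseline-to-worst shift tells more than a single post-baseline value.

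Section 17.3 also pulls in two directions. Its shift bullet covers every quantitative test with DAIDS grades, which would include lymphocytes; its haematology sentence excludes them. Two programmers could produce different tables from the same text.

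**Working it through.** No sample size, power or alpha figure is involved, so this is a comparison of lists.

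**Step 1. Compare the Appendix 4 haematology table with the SAP 17.3 list.**

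| Test | Graded in Appendix 4 | Summarised under 17.3 |
|---|---|---|
| Hemoglobin | yes | yes |
| WBC | yes | yes |
| Neutrophils | yes | yes |
| Platelets | yes | yes |
| Lymphocytes (absolute) | yes | **no** |
| Hematocrit | no | yes |
| RBC | no | yes |

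Graded: 5. Summarised: 6. Both: 4. Graded but not summarised: 5 − 4 = 1 (lymphocytes). Summarised but not graded: 6 − 4 = 2 (hematocrit, RBC).

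**Step 2. Look for another by-arm display of lymphocyte grades.** In 17.3 the DAIDS shift table is the only output that tabulates laboratory grades by arm. The remaining outputs that could carry lymphocytes are the grade 3 or higher listing and the listing of all laboratory data. Both are subject-level.

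**Step 3. Can the retained tests stand in for lymphocytes?** Take an illustrative subject, with all values in x10E9/L: neutrophils 4.3, lymphocytes 0.3, other cells 0.4, so WBC = 4.3 + 0.3 + 0.4 = 5.0. Under Appendix 4:
- WBC 5.0 exceeds 2.499: No Event.
- Neutrophils 4.3 exceed 1.000: No Event.
- Lymphocytes 0.3 are below 0.350: Grade 4.

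The retained white-cell tests would show nothing for this subject. The values are invented to test the cut-offs and are not trial data.

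**Step 4. Count coverage under each version of the plan.**
- SAP V1.0 as written: 4 of 5 graded haematology tests in the by-arm shift table.
- SAP V1.0 with lymphocytes added: 5 of 5.
- After the 16 March 2022 form: 0 of 5, because the whole laboratory summary is dropped.

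**The case against.** The strongest reply is that lymphopenia is not hidden. Listings for safety outputs are ordered by treatment received (SAP Appendix 2), and the grade 3 or higher listing, on its own wording, takes in lymphocytes. With 81 subjects randomised in Part A, a reader could count severe cases by arm. Protocol 5.6.1 also says that a grade 3/4 laboratory abnormality judged clinically significant should be reported as an adverse event. TEAEs are tabulated by treatment group and maximum severity, and the 2022 form does not remove those tables. This stands, and it rules out the inference that graded lymphopenia is never compared by arm. It does not close the gap. A listing gives no proportions. The TEAE route misses values not judged clinically significant, and Protocol 7.1 allows an event's severity grade to differ from the laboratory grade.

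A second reply is that the protocol leaves safety details to the SAP, which openly selects key parameters and plans no safety testing. That discretion is real, and only a descriptive display is affected. It does not explain why a graded test is dropped and two ungraded ones kept.

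A third reply is that the 2022 form overtakes 17.3. This is correct for the final delivery. It widens the gap to all five graded haematology tests and means that an edit to 17.3 alone is not enough.

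**Conclusion.** The point holds as a minor incompleteness in SAP V1.0. One of the five DAIDS-graded haematology tests is excluded by the wording of 17.3 from the by-arm shift table, in tension with that section's own shift bullet. What is lost is the descriptive proportion and shift by lymphocyte grade in each arm. This rests on reading the haematology restriction as governing all the tabulated summaries. If it was meant for the by-visit summaries alone, the defect is one of ambiguity, and the same edit resolves it. Part of the SAP text was not available, so it cannot be ruled out that a reason is recorded there.

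Three stronger readings are not supported:
- A reader might infer that the omission weakens the rule pausing the trial when more than 20% of subjects have related grade 3/4 abnormalities. Protocol 5.6.2 bases that rule on investigator-assessed, clinically significant events and a DSMB review, not on the tables in 17.3.
- A reader might infer a lymphocyte-specific hazard from the drug class. Protocol 1.4 names mitochondrial toxicity and nephrotoxicity and raises no lymphocyte concern for AT-527.
- A reader might take 1 of 5 as the gap in the final report. It describes SAP V1.0 only.

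**What to change.** 1. In SAP 17.3, add absolute lymphocyte count to the summarised haematology parameters, so that all five tests graded in Appendix 4 enter the by-arm DAIDS shift table and its by-visit summary is produced as for the other four.
2. For the final delivery, amend the 16 March 2022 form in one of two ways: keep the by-arm DAIDS shift table for Part A, lymphocytes included, or state plainly that this part of the Protocol 8.2.5 endpoint is not reported.

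The first change adds one parameter to table programs that the SAP already calls for. The differential is collected and the grading rules are written. The second costs either one table specified in SAP V1.0 or one sentence in the report. Neither affects sample size, alpha or data collection.
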